4.1.3. Clinical Laboratory LLOQ Values

Clinical laboratory results that are below the lower limit of quantification (LLOQ) will be imputed as half of the LLOQ.

4.1.4. Coding of Concomitant Medications and Adverse Events

All adverse events (AEs) will be coded using MedDRA terms. The number and percent of participants with any treatment-emergent AE will be presented by MedDRA SOC and PT in descending frequency of occurrence. If a participant reports more than one AE that was coded to the same SOC or PT, the participant will be counted only once for that specific SOC or PT.

4.1.5. Definition of Study Time Points

Baseline is the latest pre-dose assessment with a non-missing value on or before the date of randomization (Day 1). If time is not collected, Day 1 assessments are assumed to be taken prior to first dose and used as baseline. If baseline data are missing, no derivation will be performed, and baseline will be set to missing.

The following conversion factors will be used to convert days to weeks, months, and years: 1 week = 7 days, 1 month = 30.4375 days, and 1 year = 365.25 days.

For all randomized participants, Day 1 is the date of randomization. Day 1 is the planned timepoint for the first dose administration. Day 1 is also the start of "Week 1".

For assessments on or after the randomization date, time is calculated in days as:

Study Day = Assessment Date - Randomization Date + 1 (positive number)

For assessments prior to the randomization date, time is calculated in days as:

Study Day = Assessment Date – Randomization Date

For other time variables based on two dates, Duration (days) = End Date - Start Date + 1.

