1.2 SCHEMA

1.3 SCHEDULE OF ACTIVITIES (SOA)

1.3.1 MAIN STUDY PARTICIPANT SCHEDULE

Abbreviations: CGIC – Clinical Global Impression of Change; C-SSRS – Columbia Suicide Severity Rating Scale; ET – early termination; HACA – human anti-chimeric antibodies; NA – not applicable; PGIC – Patient Global Impression of Change; PK – pharmacokinetic; TEA – Treatment Effectiveness Assessment

^a Descriptions of assessments are in Section 8.1 (efficacy) or 8.2 (safety).

^b Study Day -1 is the day prior to the first dose. Study Day 1 is the day of the first dose.

^cVital sign measurements will be taken on dosing days starting with a pre-dose measurement (≤ 30 min prior), then 0.25, 0.5, 1, 2, and 4 hours (± 5 min) after dosing starts, and as needed afterward until normalization. Measurements will be obtained once on each non-dosing day. Each test may be repeated once at each time point if the initial result is out of range.

^dLaboratory tests require blood and urine sampling for hematology, serum chemistry, and urinalysis. Samples are to be taken 2-hr post-dose completion (± 10 min) on dose days and once per visit on non-dosing days.

^e ECGs are to be done 30-min post dose completion (± 15 min) on dosing days.

^f Quality of Life Assessments include TEA (at Screening, Days 85, 169, & 225), and PGIC and CGIC (on Days 85, 169, & 225). These assessments are to be done prior to CBT at the Week 13 visit.

^g PK samples are to be taken pre-dose (≤ 30 min prior), then 4 hr (± 10 min) after the start of each infusion on dosing days. Participants should be kept on site until 4 hr post infusion start to collect samples. All other PK samples are to be collected once each visit.

^h Doses will be given over 30 min by intravenous (IV) infusion.

ⁱ AEs will be collected by phone call at 1 day and 1 week (± 2 days) post-dose throughout the study.

^j Recovery coaching will occur weekly via phone or video.

^k Saliva drug screens will be done remotely and monitored by smartphone app.

^l Cytokine samples are to be taken pre-dose (≤ 60 min prior) on each dosing day. If a participant has an infusion reaction, cytokine sampling at 1- and 4-hours post-dose (± 10 min) should be performed.

^m Drug use assessments at Screening include the DSM5 criteria for any drugs used regularly in the past year and questions about route and frequency of METH use.

ⁿ On Days 169 and 225, DSM5 criteria should be used to assess methamphetamine only and for the past 30 days, then for the past 3 months.

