4.10.2. Clinical Laboratory Analyses

All quantitative centrally reviewed clinical laboratory results other than urinalysis results will be presented in standardized units. Both observed values and changes from baseline will be summarized for each scheduled timepoint. Figures will be used if appropriate and would include shading between the lower and upper limits of normal, as applicable.

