4.10.3. Electrocardiograms

Electrocardiogram (ECG) measurement data will be summarized descriptively by timepoint. Both observed values and changes from baseline will be summarized for each scheduled timepoint, as well as depicted in figures. Abnormal values will be indicated in listings.

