5.1. Appendix 1: Schedule of Events

Assessment a	Screening	Dosing (-2/+7 days)				Follow-up (±3 days)			ET		
Study Week	≤-1	1	5	9	13	17	21	25	29	33	NA
Study Day	-60 to -1	1 ^b	29	57	85	113	141	169	197	225	NA
Informed consent	X										
Initial evaluations											
Eligibility criteria											
Demographics											
Medical history and medications	X										
Vital signs ^c	Α										
Physical and psychiatric exam											
Urine pregnancy test											
Saliva drug screen											
Laboratory tests d	X	X	X	X	X	X	X	X			X
Electrocardiogram (ECG) e	X	X	X	X	X	X	X				
App training											
App download and tutorial	X										
Saliva drug screens until acceptable											
Quality of Life Assessments f	X				X			X		X	X
Methamphetamine Use Assessments	X							X		X	X
Randomization		X									
Blood for PK/HACA & Cytokines g		X	X	X	X	X	X	X	X	X	X
Dose administration h		X	X	X	X	X	X				
Cognitive behavioral therapy		X	X	X	X	X	X		X		
Wellness check											
Update medical history											
Update medications											
Brief psychiatric evaluation		X	X	X	X	X	X	X	X	X	X
Vital signs ^c											
Targeted physical exam											
Urine pregnancy test											
Continuous events											
AE monitoring i											
Recovery coaching j						Con	tinuous				
Self-report daily drug use by app											
Random saliva drug screens k	14.64 1		1		11 >			1.1 DI		1.	

Abbreviations: ET - early termination; HACA - human anti-chimeric antibodies; NA - not applicable; PK - pharmacokinetic

^a Descriptions of assessments are in Section 8.1 (efficacy) or 8.2 (safety).

^b Study Day -1 is the day prior to the first dose. Study Day 1 is the day of the first dose.

^c Vital sign measurements will be taken on dosing days starting with a pre-dose measurement (≤30 min prior), then 0.25, 0.5, 1, 2, and 4 hours (±5 min) after dosing starts, and as needed afterward until normalization. Measurements will be obtained once on each non-dosing day. Each test may be repeated once at each time point if the initial result is out of range.

^d Laboratory tests require blood and urine sampling for hematology, serum chemistry, and urinalysis. Samples are to be taken 2-hr post-dose completion (±10 min) on dose days.

^e ECGs are to be done 30-min post dose completion (±15 min) on dosing days.

f Quality of Life Assessments include TEA, PGIC, and CGIC.

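### The SAP default that untimed Day 1 assessments are pre-dose is wrong for laboratory tests and ECGs, which are scheduled on Day 1 only after the infusion

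*SAP*

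**What the plan says.** SAP 4.1.5 has a main rule and a fallback. The main rule takes as baseline the most recent non-missing value obtained before dosing, no later than Day 1. The fallback covers missing clock times: "If time is not collected, Day 1 assessments are assumed to be taken prior to first dose and used as baseline". It applies to every kind of assessment. The same section confirms that this is a dosing day: "Day 1 is the planned timepoint for the first dose administration".

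The schedules give the timing. For laboratory tests, protocol 1.3.1 footnote d says "Samples are to be taken 2-hr post-dose completion (± 10 min) on dose days", and SAP Appendix 1 agrees: "Samples are to be taken 2-hr post-dose completion (±10 min) on dose days". For ECGs, protocol 1.3.1 footnote e says "ECGs are to be done 30-min post dose completion (± 15 min) on dosing days", and SAP Appendix 1 gives the same timing. Protocol 1.3.2 repeats both footnotes for the PK subset. SAP Appendix 1 marks both assessments at Screening and on Day 1.

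Baseline is then used in the safety output. SAP 4.10.2 says of laboratory results: "Both observed values and changes from baseline will be summarized for each scheduled timepoint". SAP 4.10.3 says of ECGs: "Both observed values and changes from baseline will be summarized for each scheduled timepoint, as well as depicted in figures".

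**The concern.** The fallback contradicts the schedule for two assessments. A laboratory or ECG result recorded on Day 1 without a time would be labelled baseline although, if collected on schedule, it was taken after the first infusion. The Screening value, which is the only scheduled pre-dose value for both, would lose its role as the reference.

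Laboratory and ECG safety is part of a stated secondary endpoint, and protocol 4.2 describes this as the first multiple-dose study of the antibody. According to SAP 1.2 the study stopped before Cohort 2 enrolled, so the repeat-dose safety data come from Cohort 1 alone, planned at about 40 active and 20 placebo participants. If only some times are missing, one table would also mix two reference points: Screening for participants with a recorded time and a post-dose Day 1 value for the others.

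**Working it through.** The plan gives no figure on this point to reproduce. The check is of timing, followed by an identity for the change score.

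**Inputs**
- Infusion length: 30 min (protocol 1.3.1 footnote h; SAP Appendix 1 footnote h).
- Laboratory sample: 120 min after completion, window ±10 min (footnote d).
- ECG: 30 min after completion, window ±15 min (footnote e).

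**Step 1. When the Day 1 values fall.** Minutes after infusion start = infusion length + scheduled delay ± window.
- Laboratory: 30 + 120 ± 10 = 140 to 160 min.
- ECG: 30 + 30 ± 15 = 45 to 75 min.

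The infusion ends at 30 min. Even the earliest allowed ECG, at 45 min, comes after it. No on-schedule Day 1 laboratory sample or ECG is pre-dose.

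**Step 2. Whether the default is wrong everywhere.** It is not. Vital signs, PK, HACA and cytokine samples all have a scheduled pre-dose collection on Day 1. The default is too broad by two assessments.

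**Step 3. Effect on one participant.** Let Y0 be the Screening value, Y1 the post-dose Day 1 value and Yt the value at a later visit.
- Time recorded: baseline is Y0, so the reported changes are Y1 − Y0 on Day 1 and Yt − Y0 later.
- Time not recorded: baseline is Y1, so the reported changes are Y1 − Y1 = 0 on Day 1 and Yt − Y1 = (Yt − Y0) − (Y1 − Y0) later.

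Whatever moved between Screening and the Day 1 sample is subtracted from every later visit. A shift that appeared on Day 1 and then stayed constant would be reported as no change.

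**Step 4. Effect on a group mean.** Assume that a fraction f of participants has no recorded time and that missing times are unrelated to the result. With mean changes from Screening of e1 on Day 1 and et at visit t:
- reported Day 1 mean = (1 − f) × e1
- reported mean at visit t = et − f × e1

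| f (assumed) | Reported Day 1 mean | Reported mean at visit t |
|---|---|---|
| 0 | e1 | et |
| 0.10 | 0.90 × e1 | et − 0.10 × e1 |
| 1 | 0 | et − e1 |

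The documents give neither f nor e1. The table shows the range and is not an estimate.

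**The case against.** The strongest reply is that the fallback may never be used. The main rule is right: with a recorded time, a post-dose Day 1 value is excluded and Screening becomes baseline. Nothing says that laboratory or ECG times go unrecorded. Windows of ±10 and ±15 min can be checked only against a clock time, and protocol 6.1.2 has infusion start and stop times recorded. This stands as a limit on frequency. It does not settle the matter, because SAP section 1 leaves such details to the eCRF, which is not among the documents, and the SAP itself provides for times not being collected.

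A reader might infer that the whole trial's laboratory and ECG baseline is contaminated. The documents do not support that, since the fault is confined to untimed values and their number is unknown.

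A reader might also infer that an acute drug effect would be hidden. That goes too far as well:
- SAP 4.10.2 and 4.10.3 summarise observed values alongside changes, so Screening and Day 1 levels remain visible by group.
- SAP 4.10.3 flags abnormal ECG values in listings, and SAP 4.1.1 provides participant listings of the relevant eCRF data.
- Abnormal laboratory findings can be adverse events (protocol 8.3.1), and those are summarised without reference to baseline.
- Heart rate is also a vital sign, with a pre-dose Day 1 reading and readings from 0.25 to 4 hours after the start of dosing.
- The documents give no size for any acute effect at 45 to 160 min.

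Finally, it is tempting to say that a Day 1 laboratory or ECG value can never be pre-dose. Protocol 6.1.2 lets screening requirements be met on Day 1 itself, so a repeat before the infusion is possible. If it is timed, the main rule correctly makes it the baseline.

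**Conclusion.** The concern holds in a limited form. The SAP's fallback is false for untimed Day 1 laboratory and ECG values collected on schedule. For each such value the Day 1 change is exactly zero and later changes are measured from a post-dose reference. The damage is confined to descriptive change-from-baseline summaries of these two assessments. The primary ANCOVA has no baseline term (SAP 4.6.1), and the Treatment Effectiveness Assessment is analysed as change from screening (SAP 4.7.1.2).

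The number of participants affected could be none, some or all. The conclusion rests on collection within the scheduled windows and on the fallback being applied as written. It is a modest defect in a safety definition, worth correcting because the rule is wrong for the very case that it was written to cover and the correction is cheap.

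**What to change.** In SAP 4.1.5:
1. Restrict the assumption that an untimed Day 1 value precedes dosing to assessments that the schedule places before the infusion.
2. Treat untimed Day 1 laboratory and ECG values as post-dose. Their baseline is then the latest value known to be pre-dose: normally Screening, and a Day 1 value only if its recorded time is before the infusion.
3. Report Day 1 laboratory and ECG results as the first post-dose timepoint.

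It would also help to state whether the eCRF captures these times. If it always does, the edit changes no result.

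The cost is a short text change with no new data or procedures. SAP section 1 allows for amendment before database lock and for documentation in the study report afterwards. There are two small downsides. Affected participants get an older baseline, as those with recorded times normally already have. An untimed repeat that was in fact done before the infusion on Day 1 would be set aside in favour of Screening. The age of that baseline is itself unclear: protocol 1.3.2 puts Screening at Day -15 to -1, while SAP Appendix 1 puts it at Day -60 to -1. The two should be reconciled in the same amendment.

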4.2. Participant Accounting

The number of subjects who were enrolled, treated with at least one dose of study drug, who completed the study, as well as the reasons for withdrawal, will be summarized with counts and percentages by treatment group. This table will also include number of screening failures and reasons for screening failures.

4.3. Participant Disposition

The number and percentage of participants who are randomized, receive treatment, complete treatment, discontinue treatment early, discontinue study early, and complete study will be presented by treatment group. For participants who discontinue study or treatment early, the number and percentage discontinuing by reason and most recent dosing visit will be presented. The number and percentage of participants in each analysis population will also be presented.

4.4. Baseline Characteristics and Participant History

Demographic and baseline characteristics (age, sex, race, ethnicity, body weight, height, body mass index [BMI], and days per month of METH use) will be summarized by treatment group using descriptive statistics.

4.5. Study Intervention and Concomitant Medications

4.5.1. Extent of Exposure

Study drug exposure will be summarized for all participants by treatment group. Study drug exposure will be summarized as the number and percentage of participants receiving at least one dose (i.e., in the safety population) using the number randomized as the denominator. In addition, the number of participants who completed each dosing visit and the number of doses will be summarized by treatment group, using the number in the safety population as the denominator.

4.5.2. Treatment Compliance

Study drug is administered by intravenous infusion by qualified personnel who are blinded to the treatment assignment of the participant. Compliance with dosing will be verified by reference to the electronic case report form (eCRF) documentation of dosing. CBT session attendance will be documented by the site and captured in the eCRF.

4.5.3. Concomitant Medications

All concomitant medications (i.e., prescription medications, over-the-counter medications, non-prescription medications, and supplements) taken during study participation will be recorded on the eCRF. For this protocol, a prescription medication is defined as a medication that can be prescribed only by a properly authorized/licensed clinician.

The use of concomitant medications will be summarized by therapeutic class and generic medication name using descriptive statistics. Concomitant medications will include all medications taken from randomization through follow-up.

In addition, any behavioral therapy sessions with a trained provider outside the protocol will be recorded as concomitant therapy.

4.6. Primary Estimand Analysis

The primary objective of the study is to evaluate the efficacy of IXT-m200 in preventing or reducing relapse to stimulant use.

4.6.1. Main analytical approach

The primary efficacy analysis will use the ITT population and is based on a test of the mean difference between each IXT-m200 group and the placebo group in percent weeks abstinent, as estimated using an analysis of covariance (ANCOVA). The dependent variable in the model is percent weeks abstinent; the independent variables in the model are the following:

- Treatment group assignment (discrete); and
- Stratification level of past-month METH use at screening (discrete).

[figure not shown]
The data for this primary endpoint will have shown efficacy if the test of mean percent weeks abstinent between Week 5 and Week 25 shows nominal statistically significant benefit in any IXT-m200 group relative to the placebo group.

Adjusted means and standard errors for each treatment group and the estimated difference between the groups and associated 95% confidence intervals and two-sided p-values will be reported. A plot of all saliva screen results for each individual subject throughout the study will be provided. Pseudo-R code for the plot is included in Exhibit 2. The data should be divided into subsets based on the value of the saliva test value for methamphetamine, including 'positive', 'negative', 'missed', 'invalid'. If the result of a saliva screen is not one that is listed, the sponsor should be contacted to receive instruction on how to code the value. If a saliva screen test is missed, that week will be imputed assuming the participant is not abstinent. If a participant withdraws from the study, then all weeks following withdrawal will be assumed as not abstinent. For the *n* subjects, each subject should be assigned a value from 1 to *n* for the purpose of plotting. Participants will be grouped by study treatment. An example plot is available in Exhibit 3.

Exhibit 2 Pseudo-R Code for Saliva Screen Data Plot

```
points(neg placebo$DAY,neg placebo$SUBJIDN,col=rgb(0.2,0.7,0.9,1),pch=17,cex=1)
points(pos placebo$DAY,pos placebo$SUBJIDN,col=rgb(1,0.5,0,1),pch=19,cex=1)
points(miss placebo$DAY,miss placebo$SUBJIDN,col=rgb(1,0.5,0,1),pch=4)
points(inv placebo$DAY,inv placebo$SUBJIDN,col=rgb(1,0.5,0,1),pch=5)
par(mar=c(5,1,4,2))
plot(NA,NA,xlim=c(0,175),ylim=c(0,50),xlab='Study Day',ylab=',main='IXT-M200 Saliva
Screen Results',
    yaxt='n',xaxt='n')
axis(1, at=seq(0, 175, by=7))
axis(2, at=seq(0.50,by=5))
for(i in 0:15){
 polygon(c(14*i+.5,14*i+7.5,14*i+7.5,14*i+.5), c(-5,-
5,75,75),col=rgb(0,0,0,025),border=rgb(0,0,0,025))
points(neg trt$DAY,neg trt$SUBJIDN,col=rgb(0.2,0.7,0.9,1),pch=17,cex=1)
points(pos trt$DAY,pos trt$SUBJIDN,col=rgb(1,0.5,0,1),pch=19,cex=1)
points(miss trt$DAY,miss trt$SUBJIDN-22,col=rgb(1,0.5,0,1),pch=4)
points(inv trt$DAY,inv trt$SUBJIDN,col=rgb(1,0.5,0,1),pch=5)
legend(130, 50, legend=c("Negative Test","Positive Test","Missed Test",'Invalid Test'),
    col = c(rgb(0.2,0.7,0.9,1),rgb(1,0.5,0,1),rgb(1,0.5,0,1),rgb(1,0.5,0,1)),pch = c(17,19,4,5))
```

Exhibit 3 Plot of Saliva Screen Results

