1.3.2 PK SUBSET PARTICIPANT SCHEDULE

Assessment ^a	Screening	Dosing (-2/+7 days)										Follow-up (±3 days)			ET			
		≤-1	1				5	9	13	17	21			25	29	33	NA	
Study Week	≤-1	1 ^b					29	57	85	113	141				169	197	225	NA
Study Day	-15 to -1	1 ^b													169	197	225	NA
PK Sample Collection Day			2 (+1)	8 (±2)	15 (±3)	22 (±3)							142 (+1)	148 (±2)	155 (±3)	162 (±3)		
Informed consent	X																	
Initial evaluations ^p																		
Eligibility criteria																		
Demographics																		
Medical history and medications																		
Vital signs ^c																		
Physical exam																		
Psychiatric exam (e.g., C-SSRS)																		
Urine pregnancy test																		
Saliva drug screen																		
Drug use assessment via DSM-5 ^m																		
Laboratory tests ^d	X	X					X	X	X	X	X				X		X	
Electrocardiogram (ECG) ^e	X	X					X	X	X	X	X							
App training																		
App download and tutorial ^q																		
Saliva drug screens (up to 4) ^k	X																	
Recovery coaching ^j																		
Adverse Outcomes Assessment	X							X							X		X	X
Quality of Life Assessments - TEA ^f																		
Quality of Life – PGIC and CGIC ^f								X							X		X	X
METH Use Assessments ⁿ	X														X		X	X
Randomization		X																
Blood for PK ^g	X	X	X	X	X	X	X	X	X	X	X	X	X	X	X	X	X	X
Blood for HACA ^o	X						X		X						X		X	X
Blood for Cytokines ^l	X					X	X	X	X	X								
Dose administration ^h	X					X	X	X	X	X								
Cognitive behavioral therapy	X					X	X	X	X	X						X		
Wellness check																		
Update medical history																		
Update medications																		
Brief psychiatric evaluation																		
Vital signs ^c																		
Targeted physical exam															X		X	X
Urine pregnancy test																		

Assessment ^a	Screening	Dosing (-2/+7 days)										Follow-up (±3 days)			ET			
		≤1	1				5	9	13	17	21			25	29	33	NA	
Study Week	≤1	1					5	9	13	17	21			25	29	33	NA	
Study Day	-15 to -1	1 ^b					29	57	85	113	141				169	197	225	NA
Continuous events AE monitoring ⁱ Recovery coaching ^j Self-report daily drug use by app Random saliva drug screens ^k		Continuous																

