5 STUDY POPULATION

5.1 INCLUSION CRITERIA

Eligible participants will:

1. Be at least 18 years of age at the time of study consent;
2. Meet DSM-5 criteria for Substance Use Disorder associated with methamphetamine;
3. Be treatment-seeking methamphetamine users with at least 1 methamphetamine or amphetamine positive specimen during the screening period;
4. Be able and willing to read, comprehend, and give Authorization for Use/Disclosure of Health Information (HIPAA) and informed consent;
5. Be willing to comply with study instructions and dosing, agree to make all appointments, and complete the entire course of the study;
6. Agree to use protocol-specified method(s) of birth control throughout study participation;
7. Agree to adhere to Lifestyle Considerations throughout study duration (see section [5.3](#));
8. Have access to a smartphone or other device capable of supporting the study app;
9. Successfully complete app-based training program as evidenced by submission of at least 2 valid saliva drug screens when randomly assigned during the first two weeks after the Screening visit.

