8.1.4 METHAMPHETAMINE USE ASSESSMENTS

- DSM-5 criteria checklist should be used to assess participants for Methamphetamine Use Disorder and the number of criteria met. At screening the checklist should be completed for past year history. At each subsequent assessment time point (Week 25 and Week 33), the checklist should be completed for the past 30 days AND for the past 3 months, separately.
- Also at Screening, participants should be asked, “What is the main way you take methamphetamine?” Potential answers would be Smoked, Snorted, Intravenous, or Oral.
- Participants should also be asked, “How many days in the past month did you use METH?” Answers should be categorized as <18 days or ≥18 days.

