1.2. Study Design

InterveXion's protocol M200C-2201 is a Phase 2, double-blind, placebo-controlled, multiple-dose study of the safety and efficacy of monthly intravenous (IV) doses of IXT-m200 in treatment-seeking individuals with METH use disorder. The study was stopped before enrolling Cohort 2. As such, any reference to Cohort 2 in this document no longer applies, but has been retained for reference.

The study consists of two cohorts:

- In Cohort 1, approximately 60 participants will be randomized in a 2:1 ratio to IXT-m200 1.5 g or placebo (saline).
- In Cohort 2, approximately 60 participants will be randomized in a 2:1 ratio to the recommended dose of IXT-m200 or placebo based on the interim analysis at the end of Cohort 1. If the interim analysis recommends maintaining a dose of 1.5 g, then the sample size will be recalculated.

In each cohort, participants will receive either study drug (IXT-m200 at the cohort-specific dose or placebo) at the beginning of Weeks 1, 5, 9, 13, 17, and 21. All participants will also participate in seven sessions of a standardized cognitive behavioral therapy (CBT) program which will be delivered by a trained therapist; the first dose of IXT-m200 or placebo is intended to be given on the same day of initiation of CBT. For Cohort 1, the participants will participate in the CBT sessions during their monthly visits. For Cohort 2, participants will go to the clinic weekly for saliva drug tests and will participate in CBT sessions every two weeks, starting with Week 1. Participants will be followed at monthly intervals through Week 33. Cohort 1 will use app-based assessments to monitor between visits and Cohort 2 will use TLFB to monitor between visits. Schema 1.2 in the protocol displays the schematic of the study design for Cohort 1, and Appendix 1 shows the schedule of events. The first four weeks of treatment will be considered a grace period, designed to accommodate the likelihood that participants will relapse initially and experience the effects of IXT-m200. It further allows participants time to absorb and incorporate some of the skills taught by cognitive behavior therapy. METH use endpoints will be analyzed in the weeks following the grace period.

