2.2. Sample Size Determination

As this is an exploratory Phase 2A study, the sample size was not set to power the study to statistically detect any particular treatment effect. Instead, it was chosen to balance the need to gather sufficient information regarding treatment effect and variability to plan for Phase 3, while not exposing more subjects than necessary to any yet unknown safety concerns.

Still, an assessment of the potential power of the study for statistical testing is provided in Table 4. These estimates assume that cohort 2 (if conducted) receives a different dose of IXT-m200, and provide the power for comparing *each* dose group to placebo. The primary endpoint will be based on Cohort 2, but cohorts may be pooled to perform additional analyses.

Table 4. Minimum detectable difference between *each* IXT-m200 group versus the placebo group

	placebo group								
	Detectable	Examples of detectable differences with varying pooled SD							
Power	difference	20%	25%	30%					
Cohort 1/	Cohort 2 only								
$(n_1 = 40 \text{ vs})$	$s n_2 = 20$)								
0.80	$0.78 \times \text{pooled SD}$	15.6%	19.5%	23.4%					
		(3.1 more weeks)	(3.9 more weeks)	(4.7 more weeks)					
0.85	$0.84 \times \text{pooled SD}$	16.7%	20.9%	25.1%					
		(3.3 more weeks)	(4.2 more weeks)	(5.0 more weeks)					
0.90	$0.90 \times \text{pooled SD}$	18.1%	22.5%	27.1%					
		(3.6 more weeks)	(4.5 more weeks)	(5.4 more weeks)					
Cohorts 1	and 2 pooled								
$(n_1=40 \text{ vs})$	$s n_2 = 40$)								
0.80	$0.63 \times \text{pooled SD}$	12.6%	15.8%	18.9%					
		(2.5 more weeks)	(3.2 more weeks)	(3.8 more weeks)					
0.85	$0.68 \times \text{pooled SD}$	13.6%	17.0%	20.4%					
		(2.7 more weeks)	(3.4 more weeks)	(4.1 more weeks)					
0.90	$0.73 \times \text{pooled SD}$	14.6%	18.3%	21.9%					
		(2.9 more weeks)	(3.7 more weeks)	(4.4 more weeks)					

The detectable differences were calculated in SAS Proc Power using a two-sample t-test assuming equal variance a two-sided 5% alpha. SD = standard deviation.

The literature suggests that dropout rates in the study population may be up to 50% Error! Bookmark not defined, and therefore the analyses will account for missing data.

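### Saliva screens taken before randomisation are not used in any planned analysis; adding them to the primary ANCOVA would gain some precision at about 40 v 20, by an amount the documents do not fix

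*SAP*

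**What the plan says.** **Run-in.** Inclusion criterion 9 (Protocol 5.1) requires "submission of at least 2 valid saliva drug screens when randomly assigned during the first two weeks after the Screening visit". The screening column of the schedule in Protocol 1.3.2 lists "Saliva drug screens (up to 4"), with a screening window of Day -15 to -1. One footnote, describing remote testing monitored through the app, covers both the screening and the on-study screens. Protocol 8.1.2 specifies qualitative saliva screens in both periods.

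**Endpoint.** The SAP measures the percentage of 20 weeks abstinent by saliva screens. Under SAP 4.6.1 a missed screen makes the week non-abstinent, and so does withdrawal for every later week.

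**Model.** The primary ANCOVA has treatment and "Stratification level of past-month METH use at screening (discrete"). Protocol 9.4.2 has the same two terms. The stratum comes from one screening question (Protocol 8.1.4): "Answers should be categorized as <18 days or ≥18 days".

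**Elsewhere.** The run-in results do not appear among the baseline characteristics (SAP 4.4), nor in the sensitivity, secondary, exploratory or subgroup analyses (SAP 4.6.2 to 4.8 and 4.12).

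**Size.** Cohort 1 is described as "approximately 60 participants will be randomized in a 2:1 ratio to IXT-m200 1.5 g or placebo (saline"). SAP 1.2 also records that the study stopped before Cohort 2 was enrolled.

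**The concern.** The endpoint reflects two behaviours: whether the participant used stimulants, and whether the participant submitted the test. The run-in observes both before Day 1, on the same system. The two-level stratum carries no information on test submission, and within a stratum it does not separate lighter from heavier users. A measure of this kind is usually a useful ANCOVA covariate, and here it should exist for nearly every randomised participant because entry depends on it.

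Two things are at stake with about 20 placebo participants. Outcome variance that the run-in could explain stays in the error term and widens the confidence interval. The arms may also differ by chance in run-in behaviour, and the primary estimate would carry that difference. Since the baseline table omits the run-in, a reader of the report could not see such an imbalance.

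**Working it through.** **1. Reproduce the SAP's figure.** SAP Table 4 uses a "two-sample t-test assuming equal variance a two-sided 5% alpha". For n1 = 40, n2 = 20 and df = 58, power comes from the noncentral t with noncentrality d / sqrt(1/40 + 1/20), where d is the difference in SD units. Solving for d gives 0.780, 0.835 and 0.903 SD at 80%, 85% and 90% power. The SAP states 0.78, 0.84 and 0.90, so the table reproduces.

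**2. Cost of a useless covariate.** Adding the stratum and one covariate lowers df from 58 to 56. With no correlation, the detectable difference at 80% power moves from 0.780 to 0.781 SD.

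**3. Gain from a useful one.** Let r be the partial correlation of the run-in score with the endpoint, given the stratum.
- Residual SD is multiplied by sqrt(1 - r²).
- Gain in effective sample size = 1/(1 - r²) - 1.
- Detectable difference = 0.781 × sqrt(1 - r²).

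The documents do not give r, so it is varied:

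| r | sqrt(1 - r²) | Gain in effective n | Detectable difference, 80% power | In points at SD 30% | Power at 0.78 SD |
|---|---|---|---|---|---|
| 0.10 | 0.995 | 1% | 0.777 SD | 23.3 | 80.3% |
| 0.20 | 0.980 | 4% | 0.765 SD | 22.9 | 81.5% |
| 0.30 | 0.954 | 10% | 0.745 SD | 22.3 | 83.5% |
| 0.40 | 0.917 | 19% | 0.716 SD | 21.5 | 86.3% |
| 0.45 | 0.893 | 25% | 0.697 SD | 20.9 | 88.0% |

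At SD 30% the SAP's own figure is 23.4 points. On 60 participants, the gain is worth about 60 × 0.01 = 0.6 to 60 × 0.254 = 15 extra participants.

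**4. Chance imbalance.** For a standardised baseline variable the difference between arms has standard error sqrt(1/40 + 1/20) = 0.274 SD. By the normal distribution, the chance of a gap above 0.3 SD in either direction is about 27%, and above 0.5 SD about 7%. A one-standard-error gap moves the estimate without run-in adjustment by r × 0.274 SD: 0.027 SD at r = 0.1 and 0.123 SD at r = 0.45. At SD 25% that is 0.7 to 3.1 percentage points.

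**5. Plausible r.** Illustrative simulations used two to four binary run-in screens, entry requiring a positive specimen, a noisy binary stratum, and dropout mostly of 30% to 50% scored as non-abstinent. Scoring the run-in as the share of positive tests gave r of about 0.12 to 0.25. Scoring it as submitted, valid and negative gave about 0.13 to 0.46, depending on the assumed spread of use and persistence of behaviour. In one set of these settings, r was 0.13 to 0.31 where the endpoint SD was about 20% or more, which is the range SAP Table 4 considers. These runs show what is possible; they are not evidence about this trial.

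**The case against.** **Nothing is invalid.** Randomisation is stratified, the stratum is in the model, and chance imbalance is already reflected in the standard error. SAP 2.2 says the sample size was not set to detect a particular effect, and p-values are nominal. This stands. A reader might infer that the planned estimate is biased, and the documents do not support that. The exploratory status does not remove the gain, because an information-gathering study also benefits from a narrower interval.

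**The results are not thrown away.** A reader might infer that the run-in data are discarded. They decide inclusion criterion 9 and can supply the positive specimen for criterion 3. They are unused only in the analysis.

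**The gain may be small.** The covariate rests on two to four qualitative tests in people who had to have a positive specimen, so many will score zero. Scoring positive, missed and invalid screens alike also hides differences in compliance among heavy users. The screens are listed under app training, so early misses may partly reflect learning. All of this stands, and it is why no single figure, such as a 10% to 14% cut in variance, can be taken as the size of the loss.

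**Run-in compliance is not shown to vary widely.** Two valid screens out of up to four might suggest a spread from 50% to 100%. That presumes everyone was assigned four; a participant assigned two and returning two complied fully.

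**Changing the primary model late has a price.** The SAP is dated 01 May 2024 and already records the stop before Cohort 2. SAP 2.4 planned an unblinded efficacy interim, and SAP 2.4.1 says the sponsor may have group-level data. A change now could look post hoc. This stands and shapes the fix.

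**Conclusion.** The omission is clear from the documents: a pre-randomisation measure of the outcome is collected for nearly all randomised participants, and no analysis uses it. The direction is also clear. Adjustment improves precision if the run-in predicts the endpoint and costs almost nothing if it does not. The size is uncertain. For r between 0.1 and 0.45 given the stratum, the gain in effective sample size is about 1% to 25%, and the detectable difference at 80% power is about 0.78 to 0.70 SD. The gain is negligible at the bottom of that range and becomes worthwhile from about r = 0.3 upward. These figures assume 40 v 20, a linear relation with equal variance, and a run-in score available for essentially everyone.

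This is a cheap efficiency improvement and not an error in the planned test. SAP Table 4 is correct as stated.

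**What to change.** Amend SAP 4.6.1 before database lock to add one continuous covariate: the proportion of assigned run-in screens that were submitted, valid and negative, with missed or invalid counted as not negative, as for the endpoint. Keep treatment and stratum, and report the stratum-only model alongside.

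The definition needs two details:
- **Denominator:** the screens actually assigned to that participant before randomisation.
- **Window:** Protocol 1.3.2 has Day -15 to -1 and at most four screens. SAP Appendix 1 has Day -60 to -1 and sets no cap, with screening tests continuing until satisfactory. The two must be reconciled first.

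Add the run-in results to the baseline table (SAP 4.4). Record the change in SAP 4.13, which now says nothing departs from the protocol.

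State the blinding status of those making the change. If treatment-level interim results have been seen, keep the current model as primary and prespecify the adjusted model as a supportive analysis.

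The cost is one derived variable from data already collected, one degree of freedom (0.780 to 0.781 SD at worst, counting the stratum's as well), a coarse covariate whose gain may prove small, and documentation of timing.
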